Study Detail	
Population/Indication(s):	Patients with cutaneous CD30+ lymphoproliferative disorders
Phase:	Pilot study
Sample Size:	Expected: 12, Maximum: 14
Estimated Accrual Duration:	3 years
Estimated Study Duration	Up to 5 years
Participant Duration:	Up to 24 months (12 months of treatment + 12 months of follow-up).
Participating Sites:	• City of Hope Duarte, CA
Study Agents:	Leflunomide, commercially available ...
Sponsor:	City of Hope
Industry Partner:	PendingPendingPendingPendingPendingPending
Rationale for this Study	

Cutaneous CD30 lymphoproliferative disorders include lymphomatoid papulosis and primary cutaneous anaplastic large cell lymphoma. Systemic therapies for widespread cutaneous disease include methotrexate, radiation therapy, and brentuximab vedotin, all of which have poor side effect profiles for a group of diseases that have a relatively indolent course. Leflunomide is a commercially available oral immunosuppressive agent that has been FDA approved since 1998 for the treatment of rheumatoid arthritis (RA). The primary mechanism of action of leflunomide is inhibition of de novo pyrimidine synthesis by targeting dihydroorotate dehydrogenase (DHODH), resulting in anti-proliferative effects in B- and T-lymphocytes. Leflunomide has been investigated for its anti-neoplastic potential in a variety of pre-clinical tumor models. Recent pre-clinical studies have demonstrated significant anti-neoplastic activity in CD30+ lymphoproliferative disorders. In addition, limited clinical experience is suggestive of a beneficial response when leflunomide is used to treat CD30+ lymphoproliferative disorders (CD30+LYPD). Considering the favorable toxicity profile and extensive clinical experience with leflunomide in rheumatoid arthritis, this drug represents a potential new candidate for therapy CD30 LYPDs.
	
Treatment Description	

Leflunomide will be administered orally at a dose of 20 mg/day following a loading dose of 100 mg/day for the first three days of administration. Patients will be treated in planned 28-day treatment cycles. Patients may continue to receive cycles of treatment on study (maximum 13 cycles) until disease progression or unacceptable toxicity, or other criteria for removal from study treatment are satisfied. While on active treatment patients will undergo evaluation for response after every cycle. At the time of terminating leflunomide, all participants will receive 11 days of oral cholestyramine treatment (8 g three times daily) to reduce the plasma leflunomide levels. Patient will be followed for 1 year after terminating leflunomide treatment, or until disease progression, whichever is earlier.
	
Objectives	

Primary Objective
 
• To evaluate overall response rate of leflunomide treatment 
Secondary Objectives
 
• To assess complete response rate and duration of response of leflunomide treatment• To assess toxicities of leflunomide treatment• To assess disease status by the CAILS (composite assessment of index lesion severity) 
Exploratory Ex-vivo and Molecular Objectives
	

- To generate a preliminary RNA signature associated with response of CD30+LYPD to leflunomide

Study Design

This study will be conducted as a single center, single agent pilot study.

Evaluation Criteria and Endpoints

Primary Endpoint(s):

- The primary endpoint is overall response (CR + PR). Response will be categorized by mSWAT. The response categories and criteria are summarized in Table 11.2 of the protocol.

Statistical Considerations

Sample size: This study will accrue 12 response evaluable patients, with a maximum accrual of 14 patients. Because this is a rare disease that has not been systematically studied in a prospective clinical trial, there is a lack of historical data on the response rate (and by modified severity weighted assessment tool [mSWAT]) in this patient population. The sample size for this pilot study was chosen based on feasibility considerations, and not based on any definitive statistical criterion.

With 12 patients, the 95% exact binomial confidence interval for the overall response rate will have a width of 55% (33% response rate, with 4 responders), 57% (42% response rate, with 5 responders), 58% (50% response rate, with 6 responders), 57% (58% response rate, with 7 responders), 55% (67% response rate, with 8 responders), 52% (75% response rate, with 9 responders), and 46% (83% response rate, 10 responders) respectively. For any AE with a true incidence of 15% or higher, with 12 patients there is at least an 86% chance of observing 1+ patients with such AE.

We project to accrue approximately one patient every 3 months. The projected study accrual duration is therefore 3 years.

Analysis: Observed toxicities will be summarized in terms of type (organ affected or laboratory determination), severity, attribution, time of onset, duration, serum concentration of the active leflunomide metabolite, probable association with the study treatment and reversibility or outcome. Baseline information (e.g. the extent/type of prior therapy) and demographic information will be presented as well to describe the patients treated in this study.

Rates and 95% Clopper Pearson binomial confidence interval (CI) will be calculated for overall response rate (patients that have confirmed CR or PR) and clinical benefit rate (patients that have confirmed CR/PR/MR or SD). In addition, sub-analyses will be performed where participants will be considered evaluable for response if they are confirmed eligible, receive at least 75% of leflunomide during the first cycle of therapy and have their disease re-evaluated. Response rates will also be explored based on number/type of prior therapy(ies) and serum concentration of the leflunomide metabolite (μ g/mL). Time to response and survival will be estimated using the product-limit method of Kaplan and Meier.

Preliminary molecular profiles for mRNA will be derived from skin biopsies. These profiles will be used to identify molecular correlates of therapeutic response using pathway identification and supervised principal components analysis.

Abbreviated Eligibility Criteria

Main Inclusion Criteria

- Adult patients with a diagnosis of CD30+LYPD with life expectancy of > 3 months
- ECOG ≤2
- Relapsed or refractory to at least 1 prior line of therapy
- Platelet count \geq 50,000/ μ L, ANC \geq 1000/mm³, AST and ALT < 2.0 x ULN, total bilirubin < 1.5 x ULN

Main Exclusion Criteria

- Prior treatment with lenflunomide
- Prior diagnosis of rheumatoid arthritis
- Prior allogeneic transplant
- Acute active infection, known HIV, HBV, HCV infection
- Preexisting liver disease

- History of allergic reactions attributed to compounds of similar chemical or biologic composition to leflunomide or cholestyramine.
- Non-hematologic malignancy within the past 3 years aside from the following exceptions:
 - adequately treated basal cell or squamous cell skin cancer
 - carcinoma in situ of the cervix
 - prostate cancer < Gleason Grade 6 with a stable PSA
 - successfully treated in situ carcinoma of the breast

Investigational Product Dosage and Administration

Leflunomide will be administered orally at a dose of 20 mg/day following a loading dose of 100 mg/day for the first three days of administration.

Clinical Observations and Tests to be Performed

- Clinical observations will include tolerance as well as response to treatment.
- Baseline studies will include: history and physical, skin biopsies (the skin biopsy will be used for clinical assessment and leftover samples will be used for correlative laboratory studies), as well as a laboratory evaluation to include CBC with differential, comprehensive chemistry panel (to include LDH, magnesium, phosphorus and uric acid).
- Clinical observation of response will take place on day 1 of each 28-day cycle. Subjects will be evaluated through clinic visits and physical exams as well as laboratory tests to include CBC with differential, comprehensive chemistry panel. Blood tests will be performed at a minimum of every 28 days but may be done more frequently as clinically indicated.
- Skin biopsy will be performed at the baseline, after 1 month, 4 months of Leflunomide therapy and at end of therapy (if lesions are present), and at disease progression.
- Patients will undergo toxicity assessment every two weeks for the first three cycles following initiation with leflunomide and will undergo, at a minimum, monthly toxicity assessments thereafter.

TABLE OF CONTENTS

SECTION	PAGE
Protocol Team	2
Study Schema	3
Protocol Synopsis	4
Table of Contents	7
Abbreviations	9
1.0 Objectives	10
1.1 Primary Objective	10
○ To evaluate overall response rate of leflunomide treatment	10
1.2 Secondary Objectives	10
1.3 Exploratory Objectives	10
2.0 Background.....	10
2.1 Introduction/Rationale for Development	10
2.2 Leflunomide	10
2.3 Preclinical Studies of Leflunomide as an antineoplastic agent	11
2.4 Background for Correlative Studies	12

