5.2 Cycle Definition

The planned cycle length is 28 days. Leflunomide will be taken orally once daily. Missed or held doses will not be made up. The day count continues despite a hold in agent administration. Day 1 safety assessments must be reviewed prior to the initiation of the cycle. **For a cycle to commence, the participant must be actively taking study agent.** Windows for procedures are detailed in [Section 10.0](#).

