5.6 Duration of Therapy and Criteria for Removal from Protocol Therapy

Patients will receive study treatment for a maximum of 13 cycles until disease progression, unacceptable toxicity or other criteria for removal from study treatment are satisfied. Participants may be removed from treatment for any of the following reasons:

- Evidence of disease progression per mSWAT (see [Appendix C](#))
- Participant receives 13 cycles (~ 12 months of protocol therapy)
- Patient is deemed intolerant to study treatment because of toxicity, despite dose modification/delay
- Participant withdraws from the treatment phase of the study
- General or specific changes in the participant's condition, including non-compliance, which renders the participant unacceptable for further treatment in the opinion of the treating investigator.

Documentation of the reason for discontinuing therapy and the date effective should be made in the medical record and appropriate eCRF. The participant should then proceed to off-treatment procedures for safety monitoring, leflunomide elimination and follow-up procedures. The participant's status is to be modified in the OnCore system once the off-treatment period is completed. Alternative care options will be discussed with the participant.

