10.0 STUDY CALENDAR

Table 10 describes required procedures. All procedures may increase in frequency if clinically indicated or oriented following toxicity. Adjustments to the treatment cycle due to a hold in study agent are detailed in [Section 5.2](#).

Table 10.0 Study Activity Calendar

	Screen -ing ^a	Cycle 1, 2, 3		Cycle 4+ Day 1 ^d	End of Treatment ^e				Active Follow-Up ^j
		Day 1 ^b	Day 14 ^c		Day 0 ^f	Days 1-11 ^g	Day 14 ^h	Day 30 ⁱ	
Informed Consent ^k	X ^s								
Inclusion/Exclusion Criteria ^l	X								
Registration ^m	X ⁿ								
Medical history ⁿ	X								
Physical exam	X	X		X				X	
Vital signs ^o	X	X		X				X	
Adverse events assessment ^p		X	X	X	X	X		X	
Concomitant meds review	X	X		X	X			X	
ECOG status (Appendix A) ^q	X	X		X				X	
Pregnancy test ^q	X								
TB antigen test ^r	X								
Hepatitis A, B, C testing	X ^s								
Skin photographs ^t	X	X		X	X			X	X
mSWAT ^u	X	X		X	X			X	X
Skin biopsy ^v		X ^w		X ^w				X ^w	
CBC with differential ^x	X	X	X	X				X	X
Chemistry panel ^y	X	X	X	X				X	X
Response assessment ^z		X		X	X			X	X
Teriflunomide clinical testing ^{aa}				X			X ^{dd}	X ^{dd}	
Leflunomide administration ^{bb}		Daily							
Cholestyramine ^g						X ^g			

- a. All screening procedures to be performed within 21 days of start of study agent except informed consent, acute hepatitis panel, skeletal survey which may occur within 30 days of start of treatment (footnote u) and except for registration which must occur within 7 days from start of treatment (footnote n).
- b. Day 1 assessments to be performed within 5 days (120 hours) prior to Day 1 drug (except footnote u for C1 only). Day 1 safety assessments must be resulted and reviewed prior to administration of agent for the cycle that is initiating. Screening assessments, if performed within this aforementioned time frame, may serve as C1D1 assessments. Note: items with footnote "aa" are not performed for C1D1; the windows for screening assessments still apply.
- c. Day 14 evaluations have +/- 3 day window.
- d. Day 1 assessments to be performed within 5 days (120 hours) prior to Day 1 drug. Day 1 safety assessments must be resulted and reviewed prior to administration of agent for the cycle that is initiating.
- e. Reasons to end study treatment include disease progression and unacceptable toxicity. See Section 5.8 for all criteria.

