- f. End of Treatment (EOT) Day 0 is defined as the day the determination to end treatment is made. EOT Day 0 assessments to be performed as soon as feasible, especially in the event of off treatment due to unacceptable toxicity and no later than 7 days after decision to end treatment; assessments performed after last dose of study agent(s) and within 7 days of the decision to end treatment may serve as EOT Day 0 assessments.
- g. EOT Day 1 is defined as the day cholestyramine administration begins; it will usually follow immediately after EOT Day 0, although it will not be deviation if this does not occur. If it does not follow immediately after EOT Day 0, the rest of calendar will follow per the actual EOT Day 1 (not EOT Day 0). Cholestyramine (8 grams three times daily for 11 days) will be administered according to [Section 5.5](#).
- h. EOT Day 14 assessments must occur after completion of cholestyramine, and may occur on Day 14 +/- 3 day window. If the cholestyramine administration period is extended beyond 11 consecutive days, the EOT Day 14 assessments may occur outside of this defined window.
- i. EOT Day 30 visit has a +/- 2 day window, however this window may be adjusted without deviation to ensure that it corresponds to the final teriflunomide clinical test (see footnote ee). All participants will be followed until resolution or stabilization of any serious adverse events occurring during treatment or starting within 30 days of last study drug administration or within the time to complete the EOT Day 30 assessments, which every occurs later.
- j. Active follow-up will occur for participants who have completed EOT procedures and yet to demonstrate disease progression. Disease response will be assessed every 3 months. Active follow-up will continue for 12 months or until disease progression, whichever is earlier.
- k. Informed consent process to be fully documented: e.g. prospective participant had sufficient time for deliberation, all questions were answered, treatment options provided by MD, full study reviewed including risks, and a copy of signed consent given to participant.
- l. Inclusion/exclusion criteria are detailed in [Section 3](#).
- m. See [Section 4.3](#) for slot reservation and registration process. Treatment must begin within 7 days of registration. Documentation providing Investigator's confirmation that all eligibility criteria are met must be available prior to registration.

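### Synopsis minimum of a blood test every 28 days is not carried through the end of treatment in Table 10.0: a patient completing a final cycle from cycle 4 onward has about 57–58 days between scheduled panels

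*Combined protocol and SAP*

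**What the plan says.** The Protocol Synopsis, under Clinical Observations and Tests to be Performed, has one item on visits during treatment. It opens with "Clinical observation of response will take place on day 1 of each 28-day cycle", names CBC with differential and the comprehensive chemistry panel as the laboratory tests, and closes with "Blood tests will be performed at a minimum of every 28 days but may be done more frequently as clinically indicated".

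Section 10.0 says "Table 10 describes required procedures". In Table 10.0 the rows "CBC with differential" and "Chemistry panel" have the same pattern:

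- **Marked:** screening, Day 1 and Day 14 of cycles 1–3, Day 1 of cycle 4 onward, EOT Day 30, active follow-up.
- **Blank:** EOT Day 0, EOT Days 1–11, EOT Day 14.

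EOT Day 0 is not an empty visit. It carries adverse event assessment, medication review, skin photographs, mSWAT and response assessment. Footnote f adds: "EOT Day 0 assessments to be performed as soon as feasible, especially in the event of off treatment due to unacceptable toxicity".

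Section 5.2 says "The planned cycle length is 28 days". Section 5.6 says "Patients will receive study treatment for a maximum of 13 cycles", so no cycle 14 Day 1 draw follows cycle 13.

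**The concern.** On treatment, each Day 1 panel closes the preceding 28 days of dosing. The last dosing interval has no such panel when the patient completes the cycle and stops. The next scheduled CBC and chemistry come after the planned 11-day cholestyramine course.

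Toxicity is a secondary objective (Section 1.2), to be summarised by type, grade, time of onset, duration and attribution (Section 12.4). Section 14.2 records all grade 2 or higher events through EOT. The dose-modification table (Table 7.1.1) acts on ANC, platelets, ALT/AST and bilirubin, which can change without symptoms. An adverse event assessment at EOT Day 0 without a panel cannot grade such a change.

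Attribution is also affected. Section 6.2 lists abnormal hepatic function tests and anemia among the expected cholestyramine toxicities, and Section 6.1 lists elevated hepatic enzymes and anemia for leflunomide. If an abnormality is first seen at EOT Day 30, with no panel taken between the last doses and cholestyramine, its onset and cause are hard to assign. With about 12 patients, one missed event is visible in the summary.

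**Working it through.** This is calendar arithmetic; no sample-size formula applies.

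**Inputs**

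- Cycle length 28 days (Section 5.2); at most 13 cycles (Section 5.6).
- Day 1 panels drawn 0 to 5 days before Day 1 drug (Table 10.0, footnotes b and d).
- EOT Day 0 is the day of the decision to stop (footnote f). EOT Day 1 is the first cholestyramine day, usually the next day (footnote g), so EOT Day 30 falls 30 days after EOT Day 0.
- EOT Day 30 window ±2 days (footnote i).
- Cholestyramine for 11 days (Section 5.5).

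**The plan's own figure.** From one Day 1 to the next is 28 days nominally, so the synopsis figure is reproduced while treatment continues. In cycles 1–3 the Day 14 panel divides this into 13 and 15 days.

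**Across the end of treatment.** Gap = (days from last scheduled panel to EOT Day 0) + 30.

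| How treatment ends | Days to EOT Day 0 | Gap |
|---|---|---|
| Completes a cycle from cycle 4 onward, EOT Day 0 on the last dosing day | 27 | 27 + 30 = 57 |
| Same, EOT Day 0 on what would be the next Day 1 | 28 | 28 + 30 = 58 |
| Stops on day 15 of a cycle from cycle 4 onward | 14 | 14 + 30 = 44 |
| Completes one of cycles 1–3 after the Day 14 panel | 14 or 15 | 44 or 45 |
| Stop decided at a Day 1 visit with blood drawn | 0 | 30 |

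**Windows, for the first two rows.** Shortest: 57 − 2 = 55 days. Longest: 58 + 5 + 2 = 65 days. Neither the start of cholestyramine nor the Day 30 visit is rigidly fixed (footnotes g and i), so 65 is not a strict upper bound.

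**From the last dose.** The first scheduled panel is about 30 days later, which is 30 − 11 = 19 days after an uninterrupted cholestyramine course.

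**Counting any blood test.** The only earlier EOT blood test is the teriflunomide level at EOT Day 14. It is not a toxicity panel. If it is counted, a completer's interval is 27 + 14 = 41 or 28 + 14 = 42 days, still above 28.

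**With a panel at EOT Day 0.** The 58 days would divide into 28 and 30. The last dosing interval would be closed, but the second part would still exceed 28 days slightly.

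**The case against.** The strongest reply concerns scope. The 28-day sentence stands in an item about visits in treatment cycles, and Table 10.0 meets it from Day 1 to Day 1. Active follow-up visits are every 3 months (Section 5.7), so the sentence cannot govern the whole study. This stands, and it confines the conflict to the end-of-treatment transition. It does not remove the conflict, because the last 28 dosing days are themselves on treatment and have no scheduled closing panel.

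A second reply is that both the synopsis and Section 10.0 allow extra tests when clinically indicated. A stop for an abnormal ALT, ANC or platelet count would also normally rest on a laboratory result already in hand. That is fair for toxicity that is suspected. It does not give systematic detection of asymptomatic change.

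A reader might infer several stronger points that the documents do not support:

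- *That toxicity goes untested for 58 days after dosing.* The 58 days run from the last Day 1 draw; from the last dose it is about 30.
- *That every patient has this gap.* Stops at other times give about 30 to 45 days in the cases computed. For a stop at a Day 1 visit with blood drawn, the last interval has already been tested. The documents do not say how many patients will complete cycle 13.
- *That the 7-day allowance in footnote f lengthens the gap.* It moves the EOT Day 0 assessments, not EOT Day 30, which is counted from the first cholestyramine day.
- *That the patient is drug-free by the EOT Day 30 panel.* Section 5.5 requires two metabolite tests at least 14 days apart to verify elimination. Finishing 11 days of cholestyramine does not establish it.
- *That a known share of events is lost.* Nothing in the documents allows this to be quantified.

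**Conclusion.** The point holds for the end-of-treatment transition. For a patient who completes a final cycle from cycle 4 onward, scheduled CBC and chemistry panels are nominally 57–58 days apart (55–65 with the Day 1 and EOT Day 30 windows), about twice the stated 28. No scheduled panel falls between the last Day 1 draw and the cholestyramine course. The gap is shorter, and in one case harmless to the last interval, for patients who stop at other times.

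The consequence is limited. Asymptomatic grade 2 or higher laboratory abnormalities arising in the last dosing interval may be missed, or be hard to date and attribute, unless an unscheduled test is done. The primary endpoint is not affected.

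The figures assume that EOT Day 1 directly follows EOT Day 0; each day of delay adds a day to the gap. They also assume that the blanks in Table 10.0 are intended. The marks in neighbouring rows fall where the footnotes and Section 5.5 lead one to expect (cholestyramine under Days 1–11, teriflunomide under Days 14 and 30), so a shifted column is unlikely.

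**What to change.** Reconcile the synopsis sentence with Table 10.0 on one question: does the 28-day minimum cover the close of the last dosing interval? Then make the EOT Day 0 column of the CBC and chemistry rows agree with the answer. Which monitoring schedule is right is for the sponsor to decide.

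- If the minimum does cover it, the table needs to show that at EOT Day 0. The cost is a calendar amendment and at most one routine draw per patient at an existing visit. The wording should also allow for the roughly 30 days that would remain from EOT Day 0 to EOT Day 30.
- If Table 10.0 stands, limit the synopsis sentence to the Day 1-to-Day 1 interval on treatment. The report should then state that, for patients without a closing or unscheduled panel, laboratory toxicity in the last dosing interval was not systematically measured. The cost is a text change.
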